7.4 MAGNETIC RESONANCE IMAGING (MRI) SCAN

The actual value and percent change from baseline of MRI measurements such as LVMI, LVESVI, LVEDI, and LVEF will be summarized by visit and treatment group using descriptive statistics. MRI measurements other than the above (e.g. liver and spleen iron content [mean hepatic T2*] and [mean splenic T2*] and cardiac T1 map) are expected from only a subset of patients.

7.5 SENSITIVITY ANALYSES

Key anemia-related PD endpoints will be summarized separately for patients with and without off protocol ESA dosing. Protocol ESA dosing is defined in [Section 2.5.1](#). The secondary and other PD endpoints based on measurements of TSAT, ferritin, CHr, hypochromic RBC, reticulocyte count, and hemoglobin will undergo the sensitivity analyses. These analyses will exclude patients who have off-protocol dosing of ESAs or iron during Weeks 1 – 4 as defined in [Section 2.5.1](#).

Because hospitalizations are associated with multifactorial reduction in hemoglobin and missed ESA doses, a sensitivity analysis will be performed of the above two analyses in which analyses of ESA doses, ERI, and hemoglobin after the start date of the first SAE will be excluded.

8. SAFETY ANALYSIS

All safety analyses will be performed on the safety analysis population. Safety data presented by treatment group will be summarized on an ‘as treated (treatment received)’ basis.

8.1 PRIMARY SAFETY ANALYSIS

The primary safety analyses will provide data that will support the characterization of the MTD or to establish that the highest dose examined did not exceed the MTD.

Number (percent) of subjects who potentially experienced DLTs (defined in [Section 1.1.2](#)) will be reported by treatment group. The Adverse Events that are used to identify DLTs will be tabulated. The Adverse Events will be summarized by preferred term, CTCAE grade and relationship to study drug. Determination of the MTD will be made by the SRC. Specifically, the sponsor will use lab listings to identify possible lab-based DLTs. Any possible DLTs will be queried to be reported as AEs by the investigator and the investigator CTCAE grade, which will include the clinical information needed for some of the CTCAE lab definitions, e.g. "if symptomatic" or "if hospitalization needed", will be used for DLT determination.

8.2 SECONDARY SAFETY ANALYSIS

Number (percent) of subjects who experienced the events of interest: Severe (\geq Grade 3) infusion-related reactions, hypersensitivity reactions during the Study Drug infusion, and/or anaphylaxis occurring at any time will be summarized by treatment group, preferred term, CTCAE grade, relatedness to the study drug and seriousness. All of these events will be identified from the Infusion-Related Reaction, Hypersensitivity, and Anaphylaxis CRF. Events on this list that appear to meet the protocol definition of hypersensitivity and anaphylaxis based on the Medical Monitor’s review will be queried if they have not already been reported on the Infusion-Related Reaction, Hypersensitivity, and Anaphylaxis CRF.

Descriptive statistics will also be reported for additional safety assessments by treatment group, including adverse events, physical examination findings of possible infection, vital signs, ECG, clinical laboratory, and anti-drug antibodies (binding and neutralizing).

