9.3 Adverse Events of Special Interest

The following adverse events of special interest must be reported to the Sponsor within 24 hours of the Investigator's awareness, even if not meeting the definition of a serious adverse event:

- Severe infusion-related reactions (see [Section 8.2](#)).
- Hypersensitivity reaction during the Study Drug infusion (see [Section 8.2](#)).
- Anaphylaxis (see [Section 8.2](#)) occurring at any time, even if considered unrelated to the Study Drug

A CRF for the collection of the details of such reactions will be available in the EDC.

Neutropenia, Grade 2 or higher [i.e., absolute neutrophil count < 1500/mm³ and decline by at least 25% from Baseline] are also events of interest and these will be separately summarized by treatment group and dose.

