9.7 Reporting of Serious Adverse Events and Adverse Events of Special Interest

The SAE reporting period is the same as the AE reporting period. All SAEs that occur during the reporting period and regardless of causality, must be reported by the Investigator to [REDACTED] by completing the SAE Form in the electronic data capture (EDC) system. Any pertinent source documents should also be submitted as soon as they are available. Do not withhold submission of an SAE even if complete information about the event is not available at the time of the initial report. Follow-up information on the SAE should be sent promptly by the Investigator when any additional relevant information about the event becomes known to the Investigator, or as requested by [REDACTED] or Corvidia Therapeutics.

SAE and Pregnancy Reporting Contact Information

Hypersensitivity reactions (see [Section 8.2](#)) occurring during the Study Drug infusion and anaphylaxis occurring anytime during Weeks 1 – 24 of the study should be reported as adverse or serious adverse events within the EDC AE and SAE CRFs within 24 hours of the site's awareness of the event. A supplemental CRF will also be completed for such events. Please submit as much information as is available with the initial report.

Corvidia Therapeutics will immediately notify the Investigator about important safety or toxicology information as it becomes available. It is the responsibility of the Investigator to promptly notify the IRB/ IEC about new and relevant safety information regarding the Study Drug, including serious adverse drug reactions involving risk to human subjects, in accordance with the applicable policies. An unexpected event is one that is not listed by nature or severity in the [Investigator's Brochure](#).

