1.2.2 Secondary Safety Endpoints

- Description of the frequency of DLTs by treatment group.
- Dose-Limiting Toxicities are identified as follows:
 1. Confirmed (i.e., at least 2 consecutive measurements) Grade 3 neutropenia and representing a decline of > 25% from baseline
 2. Serious adverse events of infection in the presence of confirmed (i.e., at least 2 consecutive measurements) Grade 2 or higher new onset lymphopenia or new onset neutropenia.
 3. \geq Grade 3 alanine aminotransferase (ALT) or aspartate aminotransferase (AST)
 4. \geq Grade 4 hematologic toxicity
 5. \geq Grade 3 non-hematologic toxicity

DLT was defined as any toxicity the relationship of which to the investigational agent cannot be ruled out as follows:

- With the exception of Grade 3 non-hematologic events, Grade 3 (or higher) CTCAE toxicity of above events having an assessed relationship to the Study Drug of “definitely”, “probably”, “possibly”, or “unlikely” will be considered DLTs.
- Grade 3 non-hematologic toxicities having an assessed relationship to the Study Drug of “probably”, or “possibly” will be considered DLTs.

Note: “non-hematologic events” refer to DLT criteria 1, 2, 3, and 5 above.

- Description of the frequency of the events of interest by treatment group. The events of interest included:
 - Severe infusion-related reactions
 - Hypersensitivity reaction during the Study Drug infusion
 - Anaphylaxis occurring at any time, even if considered unrelated to the Study Drug

Infusion-related reactions, hypersensitivity reactions, and anaphylaxis will be identifiable from a check box on the AE CRF and the CTCAE grade of the event and supported by data collected on the Infusion-related reaction/Hypersensitivity/Anaphylaxis CRF. The protocol defines hypersensitivity reactions and infusion-related reactions by their temporal relationship based on timing of onset during the study drug infusion.

- Description of additional safety assessments by treatment group: adverse events, vital signs, ECG, clinical laboratory, and anti-drug antibodies (binding and neutralizing).

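### SAP 1.2.2 and 8.2 identify the infusion-reaction, hypersensitivity and anaphylaxis events from different forms, and the back-up query in 8.2 does not clearly close the gap

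*SAP*

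**What the plan says.** The frequency of the events of interest, by treatment group and dose, is a secondary safety endpoint (Protocol synopsis and 3.1.2). Protocol 9.3 names three reaction types for expedited reporting: severe infusion-related reactions, hypersensitivity during the infusion, and anaphylaxis at any time.

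The SAP says twice how these are to be found.

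- SAP 1.2.2: the events "will be identifiable from a check box on the AE CRF and the CTCAE grade of the event", and this is "supported by data collected on the Infusion-related reaction/Hypersensitivity/Anaphylaxis CRF".
- SAP 8.2, which specifies the analysis: "All of these events will be identified from the Infusion-Related Reaction, Hypersensitivity, and Anaphylaxis CRF".

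SAP 8.2 then adds a back-up query, decided on the Medical Monitor's review. It covers "Events on this list that appear to meet the protocol definition of hypersensitivity and anaphylaxis"; these "will be queried if they have not already been reported on the Infusion-Related Reaction, Hypersensitivity, and Anaphylaxis CRF".

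SAP 8.5 summarises the same kinds of reaction by treatment group and names no source form.

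On the supplemental form itself, Protocol 9.7 speaks of hypersensitivity during infusion and anaphylaxis, and then states: "A supplemental CRF will also be completed for such events". Protocol 9.3, after listing all three types, says only: "A CRF for the collection of the details of such reactions will be available in the EDC".

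**The concern.** An endpoint that is a count needs one rule for what enters the count. Here the two sections rely on different forms. A programmer following 1.2.2 and a programmer following 8.2 could produce different numbers from the same database, and nothing in the SAP says which section prevails.

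The query looks like the step that would bring the two forms together, but the SAP does not say which list it starts from. The only source named before it is the supplemental form, and the query's trigger is absence from that same form. It also leaves out one of the three reaction types.

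At stake is the reported frequency of infusion and allergic reactions to an intravenous antibody, in dose groups so small that one patient visibly moves the percentage.

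**Working it through.** The plan states no figure on this point, so there is none to reproduce. The check sets the rules side by side, then tests the query as set logic.

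**Rules compared**

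| Place | Source of the events | Severe infusion-related reaction | Hypersensitivity, anaphylaxis |
|---|---|---|---|
| SAP 1.2.2 | AE form tick box and grade, supplemental form in support | covered | covered |
| SAP 8.2, identification | supplemental form | covered | covered |
| SAP 8.2, query | a list not defined | not named | named |
| SAP 8.5 | not stated | covered | covered |
| Protocol 9.7, duty to complete the supplemental form | – | not named | named |
| Protocol 9.3, detail form available | – | covered | covered |

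**Counts under each rule**

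Let A be the qualifying events ticked on the AE form and S the events on the supplemental form.

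- SAP 1.2.2 counts A.
- SAP 8.2 counts S.
- Events in A but not in S are counted by 1.2.2 and left out by 8.2.
- Events in S but not in A are counted by 8.2 and left out by 1.2.2.
- Neither rule can exceed the union of A and S.

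The two rules agree only if every event is on both forms.

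**The query under each reading of its list**

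- If the list is the supplemental form, the events to query are S minus S, which is empty. The query is circular.
- If the list is some AE listing, the events to query are the apparent hypersensitivity and anaphylaxis events on that listing that are not in S. The query then works for those two types.
- Under both readings, severe infusion-related reactions lie outside the query as written.

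**Size of one missed patient**

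Inputs: 8 patients on COR-001 per cohort (Protocol 3.1 and SAP 1.3.1); 2 mg given in two cohorts, 6 mg in two and 20 mg in one as of Amendment 3 (Protocol synopsis); up to six cohorts (Protocol synopsis). SAP 2.1 groups active patients by dosing regimen in the final report and by cohort for the Safety Review Committee.

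- One cohort, as for 20 mg on the doses listed at Amendment 3: 1/8 = 12.5 percentage points.
- Two cohorts, as for 2 mg or 6 mg in the final report: 1/16 = 6.25, about 6.3 points.
- All COR-001 patients in six cohorts: 6 × 8 = 48, and 1/48 = 2.1 points.

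These figures show what one omission does to a percentage. They say nothing about how likely an omission is.

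**The case against.** The strongest reply is that this is loose drafting with little practical effect. Several parts of it stand.

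- **The query probably was not meant to be empty.** Its condition makes sense only if the list is something other than the supplemental form. SAP 8.1 uses a similar pattern for dose-limiting toxicities: listings are screened and possible events are queried. A reader might infer that the safety net can never fire. The text does not establish that; it establishes that the list is undefined, and that the query is circular on one reading.
- **Events are not lost from the report.** A reader might infer that a reaction without the supplemental form goes uncounted. Any treatment-emergent event on the AE form still reaches the TEAE and SAE tables and listings (SAP 8.3). Exclusion from the 8.2 table follows only if 8.2 prevails over 1.2.2.
- **A downward bias is not proved.** It holds against the union of the two forms. Against the 1.2.2 rule the supplemental form could also add events that were never ticked, so the direction is open.
- **The forms may be linked in practice.** SAP 11 locks infusion-reaction forms by reference to the corresponding AE, which suggests pairing. The eCRFs cited in SAP 1 are not among the documents, so this cannot be checked.
- **Severe reactions are hard to overlook.** Protocol 8.2 ties them to permanent discontinuation of study drug, so they should also appear in the table of AEs leading to discontinuation.
- **No dosing decision is shown to depend on this table.** Under SAP 8.1 the dose-limiting toxicities rest on investigator-reported AEs and grades, and Protocol 4.4 does not tie its stopping rules to the 8.2 summary.

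This narrows the consequence. It does not remove the conflict between 1.2.2 and 8.2, supply the missing list, or bring severe infusion-related reactions within the query.

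**Conclusion.** The point holds in limited form. The SAP has two incompatible identification rules for one secondary safety endpoint and does not say which governs. If 8.2 governs, a reaction ticked on the AE form without a supplemental form is left out of the 8.2 table, and possibly of the 8.5 table, while it remains in the general AE tables. The safety tables could then disagree.

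Severe infusion-related reactions have the weakest backing: 8.2 counts them from the supplemental form, yet neither the requirement in Protocol 9.7 nor the SAP query names them, and Protocol 9.3 only makes a form available.

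The effect of one missed patient is 12.5 points in a group of 8 and 6.3 in a group of 16, assuming that cohorts fill with 8 active patients. The frequency of missing forms is unknown. No document gives a rate, and any assumed share would be a guess. Sample size, alpha and power are unaffected. The correction is worth making before the first database lock.

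**What to change.** Amend the SAP as follows.

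1. In 1.2.2, 8.2 and 8.5, use one rule: an event counts if it is ticked on the AE form (with CTCAE grade applied for infusion-related reactions) or recorded on the supplemental form.
2. In 8.2, define the list behind the query as the listing of all treatment-emergent AEs, reviewed by the Medical Monitor without treatment assignments.
3. Extend the query to severe infusion-related reactions.
4. Reconcile the two forms before each of the three database locks in SAP 11.
5. If a supplemental form is still outstanding after query, keep the ticked event in the count and flag it. The flag matters because Protocol 8.2 notes that some infusion reactions are hard to tell from dialysis symptoms, so a reader should be able to see which events lack supporting detail.

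The cost is SAP wording, one listing and a few more queries. The reported rate may come out slightly higher than under 8.2 as written.

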8.5 INFUSION-RELATED REACTIONS, HYPERSENSITIVITY REACTIONS, AND ANAPHYLAXIS

The infusion related reactions, hypersensitivity reactions, and anaphylaxis events will be summarized by treatment group using frequencies (number and percent of subjects).

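### SAP 1.2.2 and SAP 8.2 identify severe infusion-related reactions from different sources, and neither the form-completion sentence in protocol 9.7 nor the catch-up query in SAP 8.2 names them

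*SAP*

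**What the plan says.** Protocol 3.1.2 makes the frequency of the events of interest, by treatment group and dose, a secondary safety endpoint. SAP 1.2.2 lists three such events: severe infusion-related reactions, hypersensitivity during the infusion, and anaphylaxis at any time.

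- SAP 1.2.2 says these events "will be identifiable from a check box on the AE CRF and the CTCAE grade of the event and supported by data" from the dedicated form. The AE form identifies; the dedicated form supports.
- SAP 8.2, which specifies the table, says "All of these events will be identified from the Infusion-Related Reaction, Hypersensitivity, and Anaphylaxis CRF".
- SAP 8.5 adds a further summary and names no source: "The infusion related reactions, hypersensitivity reactions, and anaphylaxis events will be summarized by treatment group using frequencies".

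Two protocol sections deal with completing the dedicated form.

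- Protocol 9.3 lists severe infusion-related reactions among the events to be reported within 24 hours and then says: "A CRF for the collection of the details of such reactions will be available in the EDC".
- Protocol 9.7 speaks of hypersensitivity reactions "occurring during the Study Drug infusion and anaphylaxis occurring anytime during Weeks" 1 to 24, and adds: "A supplemental CRF will also be completed for such events". Infusion-related reactions are not named there.

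SAP 8.2 also has a catch-up step based on the Medical Monitor's review: "Events on this list that appear to meet the protocol definition of hypersensitivity and anaphylaxis" on that review "will be queried if they have not already been reported on the Infusion-Related Reaction, Hypersensitivity, and Anaphylaxis CRF".

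**The concern.** Two programmers who follow different sections of the same SAP could report different counts for one secondary safety endpoint, and nothing in the SAP says which section prevails. The two sources are most likely to part company for severe infusion-related reactions, because the two sentences that would bring the sources together (completion in protocol 9.7, the query in SAP 8.2) mention the other two event types only.

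A severe infusion-related reaction permanently ends a patient's dosing (protocol 4.4 and 8.2). The event-of-interest table is where a reader would look for infusion tolerability by dose, and each dose has few patients, so one event decides whether a row shows any events at all.

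**Working it through.** The documents give no figure for this point, so the check is mainly a comparison of texts.

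**Step 1. Can a severe infusion-related reaction fall outside the other two categories?** Protocol 8.2 defines hypersensitivity by involvement of skin or mucosa during the infusion. It separately says that cardiopulmonary signs such as chest pain, dyspnea or a change in blood pressure may indicate an infusion reaction. A Grade 3 reaction with dyspnea and no skin or mucosal signs is therefore not hypersensitivity under the protocol. Some such cases would be classed as anaphylaxis, since the Grade 3 anaphylaxis description in protocol 8.2 includes bronchospasm and hypotension, but not every case need be.

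**Step 2. Follow such a case through the plan.** Suppose the investigator ticks the box on the AE form, grades the event 3, and does not complete the dedicated form.

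| Text | Effect on this case |
|---|---|
| Protocol 9.3 | Form is available; completion is not expressly required |
| Protocol 9.7 | Completion sentence does not name this event type |
| SAP 1.2.2 | Counted (tick and grade) |
| SAP 8.2, source | Not counted (no dedicated form) |
| SAP 8.2, query | Not triggered (names hypersensitivity and anaphylaxis only) |
| SAP 8.5 | Undetermined (no source stated) |
| SAP 8.3 | Still in the TEAE tables by term and by highest grade |

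The two identification rules give different answers, and the query does not repair the difference.

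**Step 3. What does the query search?** The sentence in SAP 8.2 points to a list that the preceding text does not define. The only source just named is the dedicated form itself. A listing of AEs is the sensible meaning, but the SAP does not say so.

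**Step 4. What would one omitted event do to the table?** Each cohort has 8 active patients (protocol 3.3.1). Doses to date are 2 mg in Cohorts 1 and 4, 6 mg in Cohorts 2 and 3, and 20 mg in Cohort 5 (protocol 3.5.4). That gives 2 × 8 = 16, 2 × 8 = 16 and 8 active patients. Six cohorts would give 6 × 8 = 48. These counts ignore replacements and leave the dose of Cohort 6 open.

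Exact (Clopper-Pearson) 95% limits: for 0/n the upper limit is 1 − 0.025^(1/n); for 1/n the lower limit is 1 − 0.975^(1/n), and the upper limit p solves (1 − p)^n + n·p·(1 − p)^(n−1) = 0.025.

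| Active n | One event counted | Same event omitted |
|---|---|---|
| 8 | 12.5% (0.3 to 52.7) | 0% (upper limit 36.9) |
| 16 | 6.3% (0.2 to 30.2) | 0% (upper limit 20.6) |
| 48 | 2.1% (0.1 to 11.1) | 0% (upper limit 7.4) |

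This shows the effect of one omission if it happens. It says nothing about how likely one is: the documents give neither an expected number of severe reactions nor a form-completion rate.

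**The case against.** The strongest reply is that the two SAP passages can be read together. The AE tick flags the event, the dedicated form supplies the detail, and a table by preferred term, grade, relatedness and seriousness would in practice be built by linking the form to the AE record. The form carries infusion-related reactions first in its title, and protocol 9.3 covers them. A severe reaction brings permanent discontinuation, emergency treatment, an antibody sample and 24-hour reporting, so a site is unlikely to overlook a form named for it. The final eCRFs, which the SAP is to be read with, are not among the documents; if ticking the box opens the form, nothing is lost.

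Most of this stands as an argument about likelihood. It does not remove the conflict: SAP 8.2 assigns identification of all three event types to the dedicated form, and SAP 1.2.2 gives that form a supporting role.

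It is also fair to say that the Medical Monitor has no infusion-reaction definition comparable to the one for hypersensitivity. Protocol 8.2 leaves the call to the investigator because some signs resemble dialysis symptoms. That is a good reason not to search every AE on an infusion day. It is not a reason to leave unqueried a reaction that the investigator has already ticked.

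A reader might go further and make three inferences that the documents do not support:

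- That protocol 9.7 restricts the form to hypersensitivity and anaphylaxis. It does not say so; it is silent on infusion-related reactions, and protocol 9.3 includes them.
- That the SAP 8.2 query can never return anything, because it looks on the form for events missing from the form. That reading makes the sentence pointless; a missing antecedent is the more reasonable explanation.
- That severe reactions could vanish from the safety report. They remain TEAEs, should appear among AEs leading to discontinuation of study drug (SAP 8.3), and can be DLTs in Days 1 to 21.

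**Conclusion.** The point holds as a conflict between two identification rules, with a completion sentence and a query that both leave out the event type affected. The consequence is a possible under-count of severe infusion-related reactions in the event-of-interest table of SAP 8.2. The size is unknown, and it is zero if the form is always completed or if the EDC system forces it. Should one event be omitted, a row of 8 active patients changes from 12.5% to 0%, and a row of 16 from 6.3% to 0%.

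The conclusion rests on reading SAP 8.2 as written and on a severe reaction being ticked on the AE form with no dedicated form and no skin or mucosal signs. The primary safety analysis and the TEAE tables do not depend on it. This is a minor point, worth correcting because SAP 1.2.2 already contains most of the better rule.

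**What to change.** Change the wording of SAP 8.2, and of 8.5 to match:

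- Count an event if it is flagged by the AE form check box or recorded on the dedicated form. Take grade, relatedness and seriousness from the AE form.
- Query any flagged event of any of the three types that has no dedicated form.
- Replace the undefined list with the AE listing that the Medical Monitor reviews, named as such.

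Align SAP 1.2.2 so that all three sections state the same rule.

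The cost is a few sentences in the SAP and a simple check for flagged events without a form. No new patient data are needed. The downside is a few extra queries, and a box ticked in error may be counted until its query is resolved.
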